3) Preliminary data from our group indicates increased cerebellar volume in individuals with spinocerebellar disease who participate in a 6-month home aerobic program, but decreased volume for those who perform balance training. Thus, if our hypothesis is true, aerobic training may have more influence on disease progression than balance training as it directly impacts the cause of deficits, the cerebellum.

Public Health Significance: There is a critical need to determine effective treatments for hereditary cerebellar diseases. Research has shown balance and aerobic training improves symptoms for individuals with these disorders, but the mechanisms of improvement are unknown. This proposal will begin to examine the impact of both training methods on the brain. By understanding how each training method impacts cerebellar volume, microstructure, and functional connectivity, future research can more precisely target training regimens with the goal of slowing the disease progression of individuals with these devastating diseases.

Research Aims & Abstracts

AIM 1) To determine the effect of training on cerebellar volume. Individuals with hereditary spinocerebellar ataxias will be randomized to either a 6-month home aerobic or balance

training program. Structural MRI scans will be taken before and after the training programs to determine the impact of training on cerebellar volume. We hypothesize that aerobic training will slow cerebellar volume loss when compared to balance training.

AIM 2) To evaluate the long-term training effects on clinical measures of ataxia and correlate changes with cerebellar volume. SARA scores will be determined before and after each training program. They will also be taken at 3- and 6-months post-training along with structural MRI scans. Consistent with our prior research, we hypothesize that improvements in SARA scores will revert back to baseline if training is halted. We further hypothesize that changes in SARA scores will correlate with cerebellar volume changes in the aerobic group, but not with changes in the balance group.

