Exploratory Aim 3) To examine the effects of exercise on cerebellar microstructure and functional connectivity to the cerebellum. Diffusion weighted imaging and resting state fMRI scans will be taken before and after individuals with spinocerebellar disease participate in a 6-month home aerobic or balance training program. We will then use the cerebellum as our region of interest to analyze how training impacts cerebellar microstructure and functional cerebellar connections. Although the impact of training on the cerebellum has been investigated in healthy individuals, it is unclear how training will impact the degenerating cerebellum in our subject population. Thus, we will use this preliminary data to determine which cerebellar regions and functional networks are most impacted by training to form targeted hypotheses for future research projects.

STUDY DESIGN

This is a single-blinded randomized control trial. After initial testing, participants will be randomly assigned to either home balance or aerobic training for 6 months. After training, individuals will undergo post-training testing. At the post-training testing, individuals will be encouraged to continue training, but not required to as part of the study. Follow-up testing will then be conducted at 3- and 6-month post-training to evaluate the longevity of training effects.

The rationale for this study design is as follows:

1) Randomization between balance and aerobic training groups will balance known and unknown confounding factors that may influence changes in cerebellar volume. Individuals

conducting assessments will be blinded to group, but participants cannot be blinded given the nature of the intervention.

2) Although the use of an active control (balance training) as opposed to a placebo control may make it more difficult to detect differences between groups, our preliminary data made us comfortable that we would be able to detect differences. This design also allows us to examine the neural mechanisms underlying balance training effects on individuals with spinocerebellar disease in addition to aerobic training.

3) 6-months of training was used for this study because prior work in our laboratory on healthy individuals showed that 6-months of training was long enough to detect statistically significant changes in brain volume.

4) Follow-up testing was selected to start at 3 months post-training because our prior research showed that clinical effects were still seen at this timepoint.

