
Study procedures

Video Recording: We will record SARA measures in order to blind researcher to intervention. The study team will use a small hand-held recorder to video the SARA test. The video will have full facial features, but the participant's name will not be attached to the recording. Analysis of the recording will only be done by members of the research team. The recording will not be used for other purposes such as teaching or commercial purposes. The recordings will be stored in a password protected database. The recording will be destroyed upon completion of the study procedures. There is no compensation for allowing video recording. These recordings will not be used in publications. They will only be used by members of the research team for evaluation purposes.

Dynamic Gait Balance: Patients will be asked to walk 20 feet and conditions such as speed and head position will be varied as previously described. The examiner will then grade the subject's movement as detailed from Shumway-Cook & Woollacott Motor Control: Theory and Practical Applications, 1995.

Gait Speed: Participants will walk as fast as possible on a 9-m runway 3 times, and we will average the results of trials.

SARA scores: SARA is an 8-item performance based scale, yielding a total score of 0 (no ataxia) to 40 (most severe ataxia). The scores are based on patient performance of gait, stance,

sitting, speech disturbance, finger chase, nose-finger test, fast alternating hand movements and heel-shin slide.

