All analysis will be conducted blind to which intervention is being evaluated. SAS (version 9.4) will be used for all statistical analyses. We will use intention to treat principles. Demographic and clinical variables will be compared using the Wilcoxon's test and chi-squared analysis for continuous and categorical variables, respectively. The association between cerebellar volume change and SARA score change will be estimated with Spearman's correlation coefficient. We will use linear mixed-effect regression analysis to test whether change in cerebellar volume differed between training groups, controlling for age and other co-variates mentioned above as fixed effect. To account for within-subject correlation due to repeated measurement, we will include a random

intercept. If the assessment effect is significant ($p < 0.05$), post hoc analysis will be performed using pairwise comparisons between assessments.

For diffusion tensor imaging, individual ANCOVAs will be determined for FA and MD in the middle of both hemispheres for the regions of interest, with age, gender, and disease type as covariates.

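### SARA video scoring is masked to intervention only; nothing hides the visit, although Aim 2's improvement-then-reversion hypothesis is a contrast between visits

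*Combined protocol and SAP*

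**What the plan says.** Masking is described in three places, each time with respect to treatment group.

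- Study Design: the individuals "conducting assessments will be blinded to group, but participants cannot be blinded given the nature of the intervention".
- Study procedures, Video Recording: "We will record SARA measures in order to blind researcher to intervention".
- Statistical Procedures: "All analysis will be conducted blind to which intervention is being evaluated".

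On handling of the recordings, the plan states "The video will have full facial features, but the participant's name will not be attached to the recording" and "Analysis of the recording will only be done by members of the research team". The recordings are to be destroyed once the study procedures are finished. Nothing is said about visit labels, dates, scoring order or when scoring takes place.

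Aim 2 sets the schedule: "SARA scores will be determined before and after each training program", and "They will also be taken at 3- and 6-months post-training along with structural MRI scans". Its first hypothesis is "we hypothesize that improvements in SARA scores will revert back to baseline if training is halted".

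**The concern.** SARA is scored by an examiner on eight performance items, so judgement enters each score. Masking to arm keeps that judgement from favouring one arm. It does not keep it from following the visit.

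Aim 2's first hypothesis is about the visit: scores better after training than before, then worse again. The team that scores the videos has written down this trajectory in advance. If the scorer can tell a baseline recording from a post-training or follow-up one, expectation can push scores towards it in both arms. If recordings are scored in calendar order, drift in the rater's standard is confounded with time. Drift need not favour the hypothesis: a steady drift to lower scores would imitate improvement and hide reversion.

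Both arms train, so no untrained group shows what the visit alone does to the scores. What is at stake is the conclusion about improvement and how long it lasts, which is the reason given for the follow-up visits.

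**Working it through.** **1. Which comparisons a visit-related rating shift reaches.** Write the rated SARA change for participant i in arm g between two visits as D = (true change) + b + (error), where b is a shift tied to the visit and, because the rater is masked to arm, the same in both arms.

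| Quantity | Effect of b |
|---|---|
| Mean change within an arm (improvement, reversion) | Moves by the full b |
| Difference in mean change between arms | b − b = 0 |
| Spearman correlation of SARA change with volume change within an arm | None: a constant added to every D leaves the ranks unchanged |
| Aim 1 (cerebellar volume from MRI software) | None: SARA is not used |

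The correlation is affected only if the bias differs between participants. To create an association, it would also have to track volume change.

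**2. Illustration of size.** The plan states no figure on this point, so there is none to reproduce.

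Inputs:
- Alpha: 0.05, from the sample size calculation. Two-sided testing is assumed, because the plan does not state sidedness.
- Number per arm: 16 (sample size calculation), 20 (after the 20% dropout allowance, 16/(1 − 0.20) = 20) and 24 (recruitment target). These were set for cerebellar volume and serve here only as plausible group sizes.
- Shift b: 0.2, 0.3 and 0.5 SD of the within-person change. These are assumptions. The documents give no SARA SD and no rater error.
- Test: a paired t-test of one visit against another within an arm. This too is an assumption. The mixed model and its pairwise comparisons between assessments are written for cerebellar volume, and no SARA-by-visit test is named.

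With no true change, the test statistic follows a noncentral t distribution with n − 1 degrees of freedom and noncentrality b√n. The chance of a significant result is P(|T| > t(0.975, n − 1)).

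Example, n = 20 and b = 0.3: noncentrality 0.3 × √20 = 1.342, critical value 2.093, probability 24.7%.

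| Shift b (SD of change) | n = 16 | n = 20 | n = 24 |
|---|---|---|---|
| 0 | 5% | 5% | 5% |
| 0.2 | 11.6% | 13.6% | 15.6% |
| 0.3 | 20.3% | 24.7% | 29.1% |
| 0.5 | 46.5% | 56.4% | 65.0% |

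A smaller shift does less: 0.1 SD at n = 20 gives about 7%.

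**The case against.** **Silence is not unmasking.** A reader might infer that the raters know the visit. The documents do not say so. The Video Recording paragraph is short, deals largely with privacy, and describes no scoring workflow. This stands: the finding is that visit masking is not specified, not that it is absent in practice.

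**The correlation hypothesis.** A reader might infer that all of Aim 2 is compromised, including the link between SARA change and volume change. That does not follow, because a common shift leaves the within-arm Spearman coefficient where it was. The predicted contrast between arms is also helped by masking to arm.

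**The percentages.** A reader might take them as the trial's actual error rate. They show what an assumed bias would do to a test the plan does not specify for SARA. This stands. They indicate sensitivity, not an estimate. Aim 2 still cannot be answered without comparing visits in some way.

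**Direction of expectation.** Reversion is predicted only if training stops, participants are encouraged to continue, and earlier work still saw clinical effects at 3 months. A visit-aware rater may therefore have no firm expectation of decline at 3 months. This weakens the argument for that visit. It leaves the before-to-after improvement and rater drift untouched.

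**Other limits remain.** Participants are unmasked, there is no untrained arm and continued training is optional. Visit masking resolves none of these. That limits what the fix can achieve but is no reason to leave an avoidable source of bias in place.

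**Conclusion.** The point holds as a gap in the stated masking. All three masking statements are confined to group or intervention, while Aim 2's first hypothesis depends on differences between visits in an examiner-scored scale, with no untrained arm. Visit expectation or rater drift common to both arms would pass in full into the within-arm improvement and the later reversion.

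The scope is limited to that conclusion. The between-arm SARA comparison and Aim 1 are largely unaffected, as is the within-arm correlation for a shift common to all participants.

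The size cannot be fixed from the documents. If a rating shift of 0.2 to 0.5 SD of the change score occurred, a nominal 5% within-arm paired test would be significant between about 12% (0.2 SD, 16 per arm) and 65% (0.5 SD, 24 per arm) of the time with nothing truly changed. This rests on the assumed shifts, a two-sided paired t-test and 16 to 24 per arm.

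It is a worthwhile and inexpensive improvement, not a fatal flaw.

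**What to change.** Add to the Video Recording paragraph:

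- Each SARA recording is coded so that visit and date are hidden from the scorer.
- The arm-masked research-team rater scores the recordings in random visit order, in batches of participants who have completed their last visit, or all together at study end. Scoring each participant separately after that person's own last visit would not allow random order across participants.
- Scoring is finished before any recording is destroyed, and the destruction rule is timed accordingly. Once the recordings are gone, visit-masked scoring cannot be recovered.
- This video score is the SARA outcome at every assessment.

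The cost is relabelling of files, later availability of SARA scores and longer retention of the recordings. No extra participants, visits or recordings are needed, and the sample size does not change. Because faces stay visible, a rater may still recognise a participant, but random order and removed dates hide which visit is being scored.

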Resting State Functional MRI: This measure will be a primary outcome for Aim 3. The anatomical and functional data will be pre-processed and analyzed using Statistical Parametric Mapping (SPM12) and the CONN toolbox Version 14p. Functional data will be pre-processed using a slice scan time correction, realignment (motion correction), registration to structural images and spatial normalization to Montreal Neurological Institute (MNI) standardized space, smoothing with a Gaussian filter of 5.0 mm spatial full width at half maximum value. A conventional band-pass filter over a low-frequency window of interest (0.008–0.09) will also be applied to the resting-state time series. After these preprocessing steps, we will extract signal to noise from the white matter and cerebrospinal fluid by principal component analysis without affecting intrinsic functional connectivity. These components, white matter, cerebrospinal fluid, and motion parameters, will be included in the model and considered as covariates of no-interest.

To determine the region of interest within the cerebellum, a localizer scan will be performed after resting fMRI as described in MRI acquisition. We focused on the legs because gait abnormalities are the main deficits in individuals with spinocerebellar ataxia. The coordinates of the region of interest within the cerebellum will be selected on the basis of activation peaks obtained from the block design analysis. For each subject, we will obtain the mean BOLD signal of the region of interest by defining a mask around the seed in the standard space. To ensure that distortion was not present in localizer scans, we will verify that head motion does not exceed a threshold of 1mm and run a general linear model with predictors associated with the movement conditions to ensure there is not activation of voxels outside the brain.

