For resting fMRI analysis, the mean BOLD time course of the regions of interest will be used as a predictor in a multisubject general linear model to evaluate the functional connectivity of that seed with every voxel in the brain. In addition, to account for potential contributions of physiological noise, the time course of nuisance signals of white matter, cerebrospinal fluid, and six motion parameters will be included as predictors in the same general lineal model. The analysis will end with an activation map of all voxels in the brain that correlate with the seed of interest. We will minimize detection of false positives by using a cluster-corrected family wise error rate correction at $p < 0.05$. The correction procedure will use Monte Carlo simulations to calculate the probability of having a cluster of a certain size being due to chance alone. Our z-statistic images will then be projected onto the inflated template brain. The analysis will be conducted separately for pre-training and post-training scans. For further group analysis, we will use random-effects analysis to compute comparison before and after training. To investigate the strength of connectivity changes at the single-subject level, we will calculate the values for each voxel underlying the connectivity maps in individual participants. These values will represent the strength of connectivity between the seed area and individual voxels. Analyses of the distribution of the values across subjects will be done to estimate connectivity patterns.

Sample Size Calculation: 11 subjects had completed our preliminary study with structural MRI scans before and after training. The data shows a change in cerebellar volume of $-1.06\% \pm 0.53$ for the balance group, and a cerebellar volume increase of $+1.28\% \pm 1.04$ for the aerobic group. The calculated effect size was 2.34. Setting $\alpha = 0.05$ and $\beta = 0.2$ and using a conservative effect size of 1.34 and a standard deviation of 1.3 (as seen in our pilot data), we determined that we will require 16 subjects per group for this study.

Dropout and Compliance Rate: In our current study looking at 6 months of balance verse aerobic training in this population, we currently have a drop-out rate of 11.8%. Using a slightly higher drop-out rate of 20%, we will require 20 subjects per group. In addition, 85% of participants in our pilot study met training goals. Studies with similar training programs show more modest

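### White-matter and CSF nuisance components are extracted after 5.0 mm smoothing with no mask erosion stated, so the assertion that connectivity is unaffected is not supported (minor; exploratory Aim 3 only)

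*Combined protocol and SAP*

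**What the plan says.** Under Study procedures, Resting State Functional MRI, the functional data go through slice-timing correction, realignment, registration to the structural images, normalisation to MNI space and "smoothing with a Gaussian filter of 5.0 mm spatial full width at half maximum value". A band-pass filter is also applied. The next sentence sets the order for the nuisance signals: "After these preprocessing steps, we will extract signal to noise from the white matter and cerebrospinal fluid by principal component analysis". Its full claim is that "we will extract signal to noise from the white matter and cerebrospinal fluid by principal component analysis without affecting intrinsic functional connectivity". The components, with the motion parameters, "will be included in the model and considered as covariates of no-interest".

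The seed is described in the following paragraph: "we will obtain the mean BOLD signal of the region of interest by defining a mask around the seed in the standard space". That sentence does not say whether the series is smoothed, how large the mask is, or whether it is limited to cerebellar tissue.

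Under Statistical Procedures, the seed time course is the predictor of interest, and "the time course of nuisance signals of white matter, cerebrospinal fluid, and six motion parameters will be included as predictors" in the same general linear model.

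On the role of the outcome, the procedures say "This measure will be a primary outcome for Aim 3". The Research Aims section labels Aim 3 exploratory and intends its data to shape hypotheses for later projects.

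**The concern.** Smoothing replaces each voxel by a weighted average of its surroundings. White-matter and CSF voxels close to grey matter therefore carry grey-matter signal once the data are smoothed. If components computed from those voxels are treated as noise and regressed out, some of the signal that the analysis is meant to measure goes with them. The usual protections are to take nuisance signals from unsmoothed data, to erode the masks away from grey matter, or both. The plan states neither, yet asserts that connectivity is left untouched.

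At stake is the accuracy of the connectivity maps, and of the before-after comparison built on them, in an aim meant to choose networks for future study. The cerebellar volume analysis (Aim 1), the SARA analysis (Aim 2) and the sample size do not depend on this step.

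**Working it through.** The plan gives no figure for leakage, so there is none to reproduce. The only numerical input it supplies is the kernel width; mask thickness, erosion depth, seed radius and signal variances are not given and are assumed below.

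**1. Kernel.** SD = FWHM / (2√(2 ln 2)) = 5.0 / 2.355 = 2.12 mm.

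**2. Leakage at a flat boundary.** For a voxel at depth d, the share of weight from the other side is Φ(−d/2.12).

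| Depth d (mm) | 0 | 1 | 2 | 3 | 4 | 5 |
|---|---|---|---|---|---|---|
| Share from across | 50% | 32% | 17% | 8% | 3% | 0.9% |

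Mixing is thus confined to about 4 mm from a boundary. The same row shows what erosion achieves: if smoothed data were kept but masks eroded by 4 or 5 mm, the shallowest retained voxel would take 3% or 0.9% from outside.

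**3. Whole uneroded masks (assumed slabs of thickness T).** The mean share from both sides is (2/T)∫₀ᵀ Φ(−u/2.12) du.

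| T (mm) | 3 | 5 | 8 | 10 | 20 |
|---|---|---|---|---|---|
| Share from neighbours | 51% | 34% | 21% | 17% | 8% |

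**4. Effect on a correlation.** Take a true seed-target correlation of 0.40. Let L be the leaked share and k the ratio of grey-matter SD to nuisance SD, and suppose that all leaked signal is the signal shared by seed and target. Then c² = k²L²/(1 + k²L²), a = 0.40 × c², and the correlation after regression is (0.40 − a)/(1 − a).

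- L = 0.2, k = 1: c² = 0.04/1.04 = 0.038; a = 0.015; result 0.385/0.985 = 0.39.
- L = 0.5, k = 1: c² = 0.25/1.25 = 0.20; a = 0.08; result 0.32/0.92 = 0.35.
- L = 0.5, k = 2: c² = 1/2 = 0.50; a = 0.20; result 0.20/0.80 = 0.25.

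If only a quarter of c² is seed-target signal (an assumption), the first and last become 0.40 and 0.37.

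A separate simulation, with true correlation 0.50 and the leaked signal displacing the nuisance signal, gave about 0.50 at 5% leakage, 0.49 at 17%, 0.47 at 30% and 0.38 at 50%. Both calculations show little loss at low leakage and a material loss only when contamination is heavy.

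**5. Could leakage differ by visit or arm?** The pilot volume changes under Sample Size Calculation are −1.06% (balance) and +1.28% (aerobic), a gap of 1.28 + 1.06 = 2.34 percentage points. For an idealised sphere of 80 to 140 mL (assumed), the radius is 26.7 to 32.2 mm. A 2.34% volume change moves the surface by about radius × 0.0234/3 = 0.21 to 0.25 mm. Changing the slab thicknesses of 3 to 8 mm by 0.25 mm changes leakage by roughly 0.7 to 3 percentage points. In the formula of step 4, a 3-point change moves the correlation by about 0.003 to 0.012 for L between 0.2 and 0.5. Folding makes the sphere a simplification, and normalisation to MNI space may offset part of the volume change.

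**The case against.** The strongest case on the other side has four parts.

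First, a short protocol may leave mask erosion unmentioned and still use it; with 4 to 5 mm of erosion the leakage all but vanishes. This limits the size of the problem. It does not supply the missing specification.

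Second, the no-effect phrase may be only a rationale for choosing principal components. A reader might infer that the plan contradicts itself. It does not: no two statements are incompatible. The phrase is an assertion that the stated order does not secure, and that weaker criticism stands.

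Third, a reader might infer that the cerebellar seed is also taken from smoothed data and so picks up outside signal. The smoothed, normalised series is the only resting series described, so the inference is reasonable, but the text does not say it. The wording that fixes the order governs only the nuisance components. Signal from outside a seed mask may also still be cerebellar. On the seed, only the lack of specification stands.

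Fourth, a reader might infer that shrinkage or growth of the cerebellum would create a spurious difference between visits or arms. The documents do not show this. Processing is the same for everyone, and the rough calculation above gives a shift of at most about 0.012 in a correlation. The mechanism exists because volume change is itself an Aim 1 outcome, but nothing in the documents suggests that it is large.

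**Conclusion.** The point holds as a minor one. As written, the white-matter and CSF components come from data smoothed at 5.0 mm with no erosion stated, and the claim that connectivity is unaffected has no support in that order. The expected consequence is mild attenuation and reduced specificity.

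The per-voxel leakage follows from the stated kernel and a flat boundary. Everything beyond that depends on masks and variances that the plan does not give. The drop from 0.40 to 0.25 should not be read as the expected effect: it needs thin uneroded masks with 50% leakage, a 2:1 SD ratio, and every bit of leaked signal being seed-target signal. At 20% leakage and a 1:1 ratio, the loss is 0.01.

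**What to change.** In Resting State Functional MRI, change the order and name the sources:

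- Extract the white-matter and CSF principal components from the realigned, normalised, unsmoothed series, in masks eroded away from grey matter, and state the erosion rule.
- State that the seed mean is taken from the same unsmoothed series, within cerebellar grey matter, and give the mask size.
- Apply the 5.0 mm smoothing only to the voxelwise data used for the maps, identically at both visits.
- Delete the no-effect phrase, or qualify it.

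This brings smoothing-induced leakage into the regressors and seed to zero by construction; partial-volume mixing in the acquired images remains. The cost is a reordered processing step with no new data and a slightly noisier seed series.
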